# **SUMMARY AND BACKGROUND**

ADPKD is the fourth most common cause of chronic kidney disease and accounts for 5% of patients with kidney failure [1]. It is the fourth most common cause for end stage renal disease (ESRD) which typically occurs in the sixth decade of life [17]. ADPKD affects more than 600,000 Americans and 12.5 million people worldwide [2].

ADPKD is characterized by the predisposition to cyst formation and enlargement. The progressive development and enlargement of cysts leads to fibrosis of the renal parenchyma and eventually ESRD [1]. The glomerular filtration rate (GFR) remains stable for many decades due to compensatory hyperfiltration. Therefore, it is imperative to utilize alternative prognostic biomarkers to assess progression to end stage renal disease (ESRD).

Due the genetic heterogeneity in ADPKD, there is significant phenotypic variability with regard to progression to ESRD. Therefore, it is critical to use biomarkers to assess patients' risk of progression to initiate early renal protective measures and therapeutics to delay progression. Factors that suggest rapid progression include hypertension onset  $\leq$  age 35, urologic events such as hemorrhagic cysts or infection  $\leq$  age 35, multiple family members with ESRD  $\leq$  age 55, or PKD 1 mutations if genetics are known. Other objective measures of rapid progression include total kidney volume growth  $\geq$  5% per year (on 3 measurements done at least 6 months apart), GFR decline  $\geq$  2.5 ml/min/year over 5 years and Mayo Imaging Classification of Class 1C-1E. The Mayo Imaging Classification is used in patients with "typical" ADPKD in which individuals have bilateral, diffuse cystic disease. It is a validated calculator for measurement of height-adjusted total kidney volume (htTKV) and predicts trajectory of GFR and time to ESRD [1]. At present, Tolvaptan, a vasopressin V2 antagonist, is the only US Food and Drug Administration (FDA) approved drug for slowing progression of ADPKD in individuals at risk for rapid progression. However, Tolvaptan is associated with significant aquaretic effects and requires frequent lab monitoring for liver toxicity, making it challenging to prescribe.

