Study Design	Phase 1 open label single arm dietary
	intervention study
Study Center	The Ohio State University

Primary Objective	Renal MRI (non-contrast) measures of total
	kidney volume to assess disease progression,
	cyst growth/progression, and stiffness/fibrosis
Secondary Objective	Urine microalbumin, eGFR, body mass and
	composition
Number of Subjects	20 patients

Inclusion Criteria	1. Age 18-65 years old
	2. Diagnosis of ADPKD by imaging
	and/or genetic testing
	3. GFR $\geq$ 25 mg/dl
	4. Patients at risk for rapid progression
	of ADPKD: Mayo Class 1C-1E along
	with any other high risk features
	including early decline in GFR,
	hypertension onset $\leq$ 35 years of age,
	urologic events $\leq 35$ years of age,
	PKD 1 truncating mutation and
	PROPKD score of 4 or higher as
	determined by the treating physician
	5. No changes of medications within the
	last three months.
	6. Able to comply with dietary
	intervention
	7. Ability to sign informed consent
Exclusion Criteria	1. Patients currently being treated with
	Tolvaptan
	2. Diagnosed with diabetes.
	3. Pregnancy
	4. Contraindications to MRI
	5. Ketogenic diet within the last three
	months
	6. Severe kidney disease with GFR < 25
	mg/dl
	7. Unable to purchase food for the diet
	intervention
	8. Gastrointestinal disorders that will
	interfere with diet intervention
	9. Chronic alcohol or drug abuse

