# MRI Imaging protocol for htTKV:

Patients will undergo investigational Magnetic Resonance Imaging for assessment of Total Kidney Volume at baseline and 1 year of study participation. MRI specific safety screening will be performed by a qualified imaging team member prior to the imaging session. Patients will be prepared for imaging by the imaging team member and imaging will be completed over the abdominal area, imaging will last no more than one hour. Studies will be carried out using FDA approved 0.55T, 1.5T, or 3T MRI units. Imaging sequences will include 2D T2-weighted Turbo Spin Echo and 3D T1-weighted fat-water separated sequences. Intravenous contrast agent will not be administered. Images of the abdomen and kidneys will be analyzed in order to calculate height-adjusted TKV according to established practices of the Mayo Imaging Classification [1].

The presence of pre- and post-treatment MRI and laboratory tests for comparing kidney size is crucial for evaluating the effectiveness of the treatment. However, there is a potential for inter and intra-observer bias in the measurement of kidney size. To address this issue, several steps and strategies can be implemented:

**Standardized Protocols**: Develop standardized protocols for measuring kidney size that all observers must adhere to. These protocols should include specific guidelines for image acquisition, positioning of patients, and measurement techniques.

**Training and Calibration:** We have ensured that that all observers receive comprehensive training on the measurement techniques and protocols, prior to the study. This training includes both theoretical and hands-on components. Additionally, periodic calibration sessions can be organized to minimize observer variability.

Quality Control Checks: We will regularly monitor the quality and consistency of measurements throughout the study. If significant variability is observed, additional training and calibration sessions should be conducted.

Interpretation Guidelines: We have developed clear guidelines for interpreting the MRI and lab results. This can help standardize the assessment of improvement in kidney size, reducing the risk of bias in interpretation.

Documentation and Audit Trails: Maintain detailed documentation of all measurements, protocols, and observer assignments. This information can be audited to ensure compliance and identify any potential sources of bias.

Table 1 | Table of Study Procedures.

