#### DATA ANALYSIS AND STATISTICAL METHODS

The study will focus on percent change for TKV, albuminuria, and GFR pre and post the ketogenic dietary intervention. We will collect the following data for each patient including age, sex, race, baseline medications, BMI, albuminuria, GFR, and blood pressure. The univariate analysis will include the above variables and use analysis of variance to assess changes at baseline and at 12 months. Based on the univariate analysis, we will perform linear regression. Ketogenic diet administration will be forced into the model. Other variables will be chosen based on strength of the univariate analysis. Our outcome of interest will be percent change in TKV, albuminuria, and GFR. In regard to MR Imagining, we will utilize a statistical method to account for observer variability. Statistical techniques such as intra-class correlation coefficients (ICC) can quantify the level of agreement between different observers and help correct for any bias.

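### The protocol credits an ICC with correcting reading bias in kidney volume, which it cannot do, and its listed bias remedies include neither masked reading nor a same-scanner rule

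*Protocol*

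**What the plan says.** The section MRI Imaging protocol for htTKV recognises the threat: "However, there is a potential for inter and intra-observer bias in the measurement of kidney size". It then lists five remedies:

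- standardised protocols, of which it says "These protocols should include specific guidelines for image acquisition, positioning of patients, and measurement techniques";
- training before the study, with optional calibration sessions;
- quality checks, with retraining if variability is large;
- interpretation guidelines, of which it says "This can help standardize the assessment of improvement in kidney size, reducing the risk of bias in interpretation";
- documentation and audit trails, including who measured what.

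The same section names the imaging sequences and allows a choice of scanner: "Studies will be carried out using FDA approved 0.55T, 1.5T, or 3T MRI units".

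Data Analysis and Statistical Methods makes percent change in total kidney volume (TKV) an outcome of interest. On imaging it says "we will utilize a statistical method to account for observer variability", without naming the method. The only example given is the ICC, in the sentence "Statistical techniques such as intra-class correlation coefficients (ICC) can quantify the level of agreement between different observers and help correct for any bias".

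The Study Synopsis describes the design as "Phase 1 open label single arm dietary" intervention, in 20 patients.

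**The concern.** There are two linked problems.

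First, the sentence on the ICC is wrong as it stands. An ICC is a ratio of variance components. It can report how closely readers agree, but it adjusts no reading.

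Second, the bias that matters most here is a shift in the month-12 readings common to all readers, and the five remedies do not address it. Readers who know which scan follows the diet can share an expectation, and training them to a common standard does not hide that knowledge. A change of scanner between visits could also shift the reading, and the protocol permits one.

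With no control arm, nothing cancels such a shift: it is added to the estimated effect of the diet. Scanner choice also cannot be repaired at the analysis stage, so it has to be settled before the scans are taken.

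**Working it through.** **Text check.** None of the five remedies mentions masking to date or visit, and none ties a participant's two scans to one unit or field strength. No other section of the protocol supplies either safeguard.

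**Inputs.** From the protocol: 20 participants, scans at baseline and one year, and a growth scale of 5% a year. The last is the threshold in Summary and Background ("Other objective measures of rapid progression include total kidney volume growth" of at least 5% per year) and serves only as a scale. The protocol gives no expected effect, standard deviation (SD) or reading error, so all other inputs are assumptions. There is no figure of the protocol's own to reproduce.

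**1. Effect of under-reading month 12.** If true growth is g and month 12 is read low by a fraction b, observed growth is (1 + g)(1 − b) − 1. With g = 5%:

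- b = 1%: 1.05 × 0.99 − 1 = 3.95%
- b = 2%: 1.05 × 0.98 − 1 = 2.90%
- b = 3%: 1.05 × 0.97 − 1 = 1.85%

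The under-reading that makes growth look halved is b = 1 − (1 + g/2)/(1 + g):

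- g = 3%: 1 − 1.015/1.03 = 1.46%
- g = 5%: 1 − 1.025/1.05 = 2.38%
- g = 8%: 1 − 1.04/1.08 = 3.70%

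**2. Does the ICC see it?** Two simulations were run with different assumed inputs, each with 20 participants, two readers and 4,000 runs per scenario.

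*Simulation A* used an absolute-agreement ICC on month-12 volume and an SD of true change of 5 points, with and without a shared 2.38% under-reading.

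| Between-patient CV | Reader error | ICC without shift | ICC with shift |
|---|---|---|---|
| 50% | 2% | 0.9976 | 0.9976 |
| 30% | 4% | 0.979 | 0.979 (0.978 with both visits pooled) |
| 70% | 2% | 0.9985 | 0.9985 |

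In the first row, mean change falls from 5.03% to 2.53%.

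*Simulation B* assumed log-normal volumes (log SD 0.45), growth of 5% with SD 4 points, and 2% error per reading. It also calculated the ICC on percent change.

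| Bias at month 12 | Mean change | ICC on volume (absolute agreement) | ICC on percent change (absolute agreement) |
|---|---|---|---|
| none | 5.0% | 0.997 | 0.62 |
| both readers −1% | 4.0% | 0.998 | 0.63 |
| both readers −3% | 1.9% | 0.997 | 0.62 |
| both readers −5% | −0.2% | 0.997 | 0.62 |
| one reader −3% | 3.5% | 0.995 | 0.51 |
| one reader −5% | 2.4% | 0.989 | 0.40 |

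A shared shift leaves the ICC where it was. A shift in one reader lowers the absolute-agreement ICC on percent change, but the mean change remains wrong.

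**3. Unpatterned scanner mixing.** If each scan carries independent scanner error with SD s, the SD of the change becomes √(SD² + 2s²). The 95% half-width is t(19 df) × SD/√20, with t = 2.093. For SD = 5:

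- s = 0: SD 5.00, half-width 2.34 points
- s = 1: SD 5.20, half-width 2.43
- s = 2: SD 5.74, half-width 2.69
- s = 3: SD 6.56, half-width 3.07

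With s = 2, the half-width goes from 1.87 to 2.29 if SD is 4, and from 2.81 to 3.10 if SD is 6. Mixing of this kind costs precision. It biases the mean only if the change of scanner runs in one direction between visits.

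**The case against.** The best defence is that the sentence claims only help, speaks of techniques such as the ICC, and follows a commitment to a method whose detail may lie in an analysis plan not shown. The MRI section also provides for retraining when variability is large. Measuring agreement and then recalibrating the readers is a fair meaning of helping to correct. For an offset between readers, simulation B shows that an absolute-agreement ICC can raise the alarm. That much stands. But recalibration does not change volumes already recorded, and no agreement statistic can signal a shift that all readers share.

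It can also be said that masking and scanner assignment are often set in an imaging manual, and that silence in the protocol proves nothing. They may indeed be set elsewhere. However, the protocol names this bias, lists its own remedies and then relies on a statistic that cannot do the job, so the list should be complete on this point.

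Three further cautions stand. The 2.4% figure was solved backwards and shows sensitivity, not likelihood. The protocol permits a change of scanner but does not say that one will happen, and this is a single-centre study. An ICC near 0.998 is for volume. On percent change, the endpoint, it is about 0.62 under the inputs of simulation B, yet it is just as blind to a shared shift.

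**Conclusion.** The concern holds. The statement that an ICC helps to correct bias is wrong whatever numbers are assumed. The listed remedies leave the endpoint unprotected against a reading or scanner shift at month 12 common to all readers.

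The possible size rests on assumptions. At 5% annual growth, a shared under-reading of 2.4% would look like a halving of growth. Over 3% to 8% growth, the corresponding figure is 1.5% to 3.7%. The ICC on volume stays at its unbiased value, between 0.978 and 0.999 over the inputs tried in simulation A. Unpatterned scanner error with an SD of 2 points would widen the 95% half-width from 2.3 to 2.7 points if the SD of change is 5.

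The protocol does not show that such a bias is present. This is one wrong statement and a cheap improvement that should be made. It does not by itself invalidate the design.

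**What to change.** 1. **MRI Imaging protocol for htTKV:** acquire both scans of a participant on the same scanner, at the same field strength and with the same sequences. Record any exception.
2. **Same section, and Data Analysis and Statistical Methods:** after the 12-month scan, one already trained observer measures both scans of a participant for the endpoint, with date and visit masked and in random order. Where possible, this should be someone who has not read that participant's scans for another purpose. Eligibility and clinical reads, and the review of MRI results at the data review meetings, stay separate and continue as planned.
3. **Data Analysis and Statistical Methods:** delete the closing six words of the ICC sentence, which claim a bias correction. If an ICC or within-reader SD is reported, base it on masked repeat readings of a subset and present it as reliability only. One example is 10 of the 40 scans (20 participants × 2), each re-read once by the same observer and once by a second trained observer.

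Research Strategy can be read as adding an MRI at 6 months. If that scan is taken, the same rules extend to it.

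**Cost:** no extra scans or staff. Scanner booking becomes less flexible and research volumes are available later. In the example, reading time rises by 10 × 2 = 20 repeat readings on top of 40 endpoint readings, and by more if baseline scans have already been read for other purposes.

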#### STUDY MONITOTRING

# Diet Monitoring Protocol for Polycystic Kidney Disease (PKD) Study

The dietary guidelines for PKD closely align with CKD recommendations, emphasizing personalized sodium intake, starting at ~2300mg/day. In a well-formulated ketogenic diet, sodium levels may decrease due to reduced sodium-rich food consumption and the natriuretic effect of decreased carbohydrate intake. To address this, our dietary approach includes an additional 1-2 g/day of sodium, with adequate fluid intake to prevent hypovolemia and associated keto-flu symptoms. Recognizing individual variations, we aim to personalize sodium intakes within a general range of 1500-2300mg/day.

### Monitoring Strategies:

# Tailored Sodium Adjustment:

- Dietetics team to tailor sodium intake based on individual needs.
- Ongoing monitoring for signs of keto-flu, edema, rapid weight changes, and blood pressure variations.

# Study Design Checkpoints:

- Incorporate consistent 24-hour dietary recalls and habitual dietary assessments.
- Regular check-ins with a registered dietitian for personalized support and adjustments.
- Education provided for recognizing high or low sodium responses.

#### Communication with Nutritionist:

- Participants to engage with a trained nutritionist for ongoing communication.
- Participants encouraged to share adherence to the dietary approach and address any questions or concerns.

#### Objective and Subjective Markers:

- Daily monitoring of blood ketones levels to assess ketosis.
- Address deviations individually with appropriate diet counseling and support.

# Dietary Assessments:

- Submission of both acute (24-hour) and more habitual (30-day) diet assessments.
- Analysis of dietary data to ensure adherence and inform necessary adjustments.

#### Clinical Collaboration:

- Reinforce education on signs and symptoms associated with sodium balance.
- Work closely with clinicians to maintain consistent messaging and promptly address emerging issues.

This comprehensive monitoring protocol integrates various strategies to ensure effective tracking and management of the dietary approach for individuals with PKD. Regular communication,

objective markers, and collaboration with healthcare professionals contribute to a thorough assessment of diet adherence and individualized support throughout the study.

# Monitoring Plan for Polycystic Kidney Disease (PKD) Ketogenic Diet Intervention Study

# **Objective:**

The primary objective of this monitoring plan is to oversee and ensure the safety of study participants and the integrity of data collected during the Polycystic Kidney Disease (PKD) ketogenic diet intervention study. The primary marker of disease progression will be total kidney volume assessed via MRI.

#### **Information to be Evaluated:**

# **Patient Safety:**

# Adverse events related to the ketogenic diet, if any.

Monitoring of vital signs, kidney function, and electrolyte levels. Compliance with dietary recommendations and any potential side effects.

# **Data Integrity:**

Accuracy and consistency of MRI measurements of total kidney volume. Proper documentation of patient data and dietary adherence.

# **Monitoring Personnel:**

**Principal Investigator (PI):** The PI will have overall responsibility for the study and will lead the monitoring efforts.

**Key Personnel :** The study coordinator will assist in data collection, ensure compliance with the study protocol, and report any issues to the PI.

#### **Timing of Monitoring:**

# Monitoring will be conducted at the following time points:

**Baseline:** Prior to enrollment, each participant's medical history, kidney function, and MRI scans will be assessed.

**Regular Intervals:** During the study, participants will be monitored regularly. This includes assessments of dietary adherence (weekly by Key Personnel), vital signs, anthropometrics, blood work and glomerular filtration rate (GFR) will be used for monitoring disease progression at the specified intermediate time points (Baseline, Week 6 and Month 3, Month 6, Month 9, Month 12), and kidney function (Baseline, Month 12 via MRI).

**Adverse Event Reporting:** Any adverse events related to the ketogenic diet or the study protocol will be monitored continuously and reported promptly.

#### **Decisions and Actions:**

**Data Review Meetings:** The study team will conduct regular data review meetings to assess the safety and progress of participants. This will involve a review of adverse events, dietary adherence, and MRI results.

**Stopping Criteria:** The study will include predefined stopping criteria to protect participant safety. If severe adverse events related to the ketogenic diet occur or if there is a significant worsening of kidney function, the study may be halted early.

**Reporting:** All monitoring findings, decisions, and actions will be documented in a monitoring report. Serious adverse events will be promptly reported to the Institutional Review Board (IRB) and relevant regulatory authorities, as required. Detailed Adverse enevt monitoring can be found below.

**Participant Withdrawal:** If participants wish to withdraw from the study, they will be allowed to do so at any time without prejudice.

# **Early Termination:**

We anticipate that participants will follow the diet plan as closely as possible to ensure the study's success. In the event of a more than twofold increase in serum creatinine, reaching Stage II acute kidney injury, we may consider early termination from the study. However, we recognize that individual differences, especially in creatinine levels related to protein intake, may occur. Therefore, decisions about early termination will be made in consultation with a physician. Subsequent visits will involve careful consideration of the rate of increase in serum creatinine, allowing the physician to determine whether continued participation is safe and advisable for the participant's health. Our top priority is the well-being of each participant, and any decisions about early termination will be made with their best interests in mind.

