#### **OUTCOMES**

**Study Endpoints:** Change in total kidney volume (TKV) from baseline to 1 year to assess disease progression. Change in albuminuria and GFR.

**Primary Objective:** The primary Objective will be to determine htTKV at baseline and 1 year after ketogenic diet intervention.

**Secondary Objectives:** The secondary endpoints will be measurement of GFR and 24-h urine microalbumin.

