# Visit 4 (6 months):

- Same procedures in visit 1, except no MRI will be done at this visit.

Visit 5 (9 months):

- Same procedures in visit 1, except no MRI or DXA Scan will be done at this visit.

Visit 6 (12 months): Same procedures in visit 1.

- Medications
  - Vitals
- Physical Exam
- Patients will undergo MRI non-contrast for evaluation of htTKV
- Blood will be drawn for assessment of GFR, urine osmolality, and urine microalbumin to creatinine ratio
- Payment of \$500

For testing at the PAES building in the Kinesiology Laboratory, subjects will arrive at the lab in the morning after an overnight fast. We will test for hydration, measure height and body mass, and then have participants complete surveys followed by resting blood pressure. A phlebotomist will obtain blood samples from a forearm vein in subjects after sitting for 10-min. Appropriate sample tubes will be used for EDTA, sodium heparin, or serum for different analytes. A serum tube will be sent to Quest Diagnostics to assess standard chemistry panel (liver enzymes, kidney function, lipids, etc.).

Serum and plasma will be immediately centrifuged and aliquoted into tubes and stored at -80°C until subsequent analyses. Samples will be thawed only once for analysis and assayed in duplicate for ketones, glucose, and insulin, which will be used to calculate an index of insulin resistance, and HbA1c. Extra serum and plasma will be archived for future analysis of biomarkers that may provide insight into novel associations with depression.

We will determine body composition from a single whole-body scan using dual-energy x-ray absorptiometry (iDXA, Lunar Corporation, Madison, WI). Total time for this visit will be approximately 1-2 hours.

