### 5. Withdrawal of Participants from the Study

Participants may be removed from the study for any of the following reasons:

- A participant requests discontinuation;
- The Investigator initiates removal for medical or compliance reasons;
- Occurrence of any AE or condition that could, in the Investigator's opinion, interfere with the evaluation of the effect of the study beverage or put the participant at undue risk.

It is understood by all concerned that an excessive rate of withdrawals can render the study uninterpretable, therefore, unnecessary withdrawal of participants should be avoided. Should a participant decide to withdraw, all efforts will be made to complete and report observations as thoroughly as possible. In the event that a participant is withdrawn from the study, the reason for the withdrawal will be documented in the eCRF.

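### Early termination on a creatinine rise can end study follow-up, and nothing clearly secures the month-12 GFR and MRI after an investigator-decided exit

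*Protocol*

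**What the plan says.** Three parts of the protocol meet here.

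- **The exits.** Early Termination says: "In the event of a more than twofold increase in serum creatinine, reaching Stage II acute kidney injury, we may consider early termination from the", where what is left is the study as a whole. It adds that "decisions about early termination will be made in consultation with a physician" and that "individual differences, especially in creatinine levels related to protein intake, may occur". Section 5, Withdrawal of Participants from the Study, separately allows the investigator to remove someone for medical or compliance reasons, and lists as a further ground: "Occurrence of any AE or condition that could, in the Investigator's opinion, interfere with the evaluation of the effect of the study beverage". The intervention is a diet, so I read the beverage there as the diet.
- **The endpoint.** Outcomes states: "The secondary endpoints will be measurement of GFR and 24-h urine microalbumin". The synopsis lists "Urine microalbumin, eGFR, body mass and" composition. On the source of the value, Study Procedures says: "A serum tube will be sent to Quest Diagnostics to assess standard chemistry panel (liver enzymes, kidney function, lipids, etc". No measured GFR and no cystatin C is named, and no estimating equation is given.
- **The analysis.** Data Analysis and Statistical Methods takes percent change in TKV, albuminuria and GFR as the outcome and will "use analysis of variance to assess changes at baseline and at 12 months". Timing of Monitoring lists GFR at Week 6 and Months 3, 6 and 9 as well, but as monitoring; the analysis section does not bring these values into the outcome.

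On follow-up after exit, section 5 promises best efforts to complete observations, but the sentence is worded for a participant who decides to withdraw.

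**The concern.** A rule that may end study participation when creatinine more than doubles acts on the marker that very probably generates the GFR endpoint. If such a participant leaves before month 12, the percent change that the protocol defines cannot be formed from a 12-month value. Those lost would be the ones with the largest apparent GFR fall, so the mean in those who remain would look more favourable than the mean in all who started. With one arm of 20, no comparator loses participants in the same way, and a few exits can move the estimate.

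The month-12 MRI for the primary kidney-volume outcome is exposed to the same loss. This is a matter of protocol wording: a SAP can model a missing value but cannot recover an assessment that was never made.

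**Working it through.** **Step 1. Does any text secure the month-12 value after a physician- or investigator-decided exit?**

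- Early Termination: the decision concerns the study and continued participation. Stopping the diet is not separated from ending assessments.
- Section 5: the best-efforts sentence is worded for participant-decided withdrawal. Its reach to a physician's or investigator's decision is arguable at best.
- Serious Adverse Event Follow-Up: reports continue until the event resolves or stabilises, among other end points. A month-12 GFR or MRI is not required.
- MRI protocol, Table 1 and Timing of Monitoring: MRI at baseline and 12 months only. Research Strategy alone adds 6 months, and a 6-month scan would not be the 12-month value anyway.

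No passage clearly secures it.

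**Step 2. How large could the effect on GFR be?** The protocol gives no expected termination rate, SD or GFR change, so there is no figure to reproduce. Everything below except N = 20 and the twofold trigger is assumed.

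Let eGFR vary as creatinine to the power −a, with a from 1.0 to 1.2. At exactly a twofold rise the GFR change d is:

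- a = 1.0: 2^(−1.0) − 1 = −50%
- a = 1.2: 2^(−1.2) − 1 = −56.5%

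Let k participants exit under the rule, let d persist to month 12, and let the others change by m on average, from 0% to −10%.

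Mean in all 20 = (k·d + (20 − k)·m) / 20. Mean in those remaining = m. Shift = k·(m − d) / 20.

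| m | d | shift, k = 1 | shift, k = 2 |
|---|---|---|---|
| 0% | −50% | 2.50 | 5.00 |
| −5% | −50% | 2.25 | 4.50 |
| −10% | −50% | 2.00 | 4.00 |
| 0% | −56.5% | 2.82 | 5.65 |
| −5% | −56.5% | 2.57 | 5.15 |
| −10% | −56.5% | 2.32 | 4.65 |

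Example: m = −5%, d = −50%, k = 1. All 20: (−50 + 19 × −5)/20 = −7.25%. Those remaining: −5%.

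If the injury partly recovers, the shift shrinks. With a month-12 change of −25% and m = −5%, it is (−5 + 25)/20 = 1.0 point.

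**Step 3. Against sampling error.** Take m = −3%, d = −50%, k = 1: shift = 47/20 = 2.35 points. With an assumed SD of 10 among the 19 remaining, SE = 10/√19 = 2.29, so the shift is about 1.0 SE. (For SD 8 and 12 the SE is 1.84 and 2.75, giving 1.3 and 0.9.) Adding the outlying participant raises the SD: √[(18 × 100 + 0.95 × 47²)/19] = 14.3, so SE = 14.3/√20 = 3.2, and the shift is about 0.7 of that SE.

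**Step 4. Chance of at least one such participant.** 1 − (1 − p)^20, for an assumed per-person risk p: 33% at p = 2%, 64% at 5%, 88% at 10%.

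**The case against.** The case on the other side has several parts, and most of it limits the point rather than removing it.

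- **The rule is discretionary.** Termination may be considered, a physician is consulted, protein-related creatinine changes are acknowledged, and later visits weigh the rate of rise. A reader might infer that everyone whose creatinine doubles drops out, or that the GFR mean is by design computed only on those whose creatinine did not double. The text supports neither; it supports only that such participants can be lost.
- **The section 5 ground is general.** It covers any event or condition and has no kidney criterion. A kidney event could fall under it, but the ground is not itself tied to the endpoint.
- **Harm is not hidden.** An event leading to discontinuation counts as an adverse event, all adverse events are recorded, the reason for withdrawal goes in the eCRF, and significant worsening of kidney function may halt the study. At most, the harm is missing from the GFR summary.
- **Missing-data methods may sit in a SAP that is not shown.** This is right, and their absence is not the point here. Whether an assessment is sought after exit is a protocol matter.
- **The best-efforts sentence exists.** It does, and extending it is most of the remedy. As worded, it does not clearly cover an exit decided by someone other than the participant.
- **The sizes are assumed.** They are, throughout.

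**Conclusion.** The point holds as a possibility that the protocol leaves open. A more-than-twofold creatinine rise can end study participation. The GFR endpoint very probably uses the same marker, an inference from the synopsis's eGFR and the serum panel, since no equation is stated. Nothing clearly secures the month-12 value after an investigator-decided exit. If such participants are lost, the GFR result looks more favourable, by about 2 to 3 percentage points for each one in 20. That range assumes an eGFR exponent of −1.0 to −1.2, a mean change of 0% to −10% in the others, and no recovery by month 12; recovery would make it smaller.

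A reader might infer that kidney volume is biased in favour of the diet as well. The documents do not support that: nothing in them links a creatinine doubling to faster or slower 12-month volume growth, so the direction is unknown. What can be said is that the month-12 MRI may be missing for the same people. The wording should be corrected, but it does not invalidate the design.

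**What to change.** Leave the creatinine trigger and every decision about the diet with the physician, as now. Then change the wording in four places:

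1. **Early Termination and section 5:** state that, whatever is decided about the diet, the already scheduled month-12 GFR, urine tests and MRI are still sought, with consent, from anyone stopped early or removed by the investigator.
2. **Section 5:** do not use possible interference with the evaluation of effect as a reason to end outcome follow-up; record and flag the event instead. Keep the undue-risk ground as it stands.
3. **Data Analysis and Statistical Methods:** state that month-12 values obtained after an early stop enter the analysis. Use the triggering creatinine or GFR only in a sensitivity analysis, because an acute value that may recover, or may partly reflect protein intake, is not a month-12 outcome.
4. **Reporting:** give the number terminated under the creatinine rule, and their last GFR, beside the GFR and TKV results.

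The cost is a wording amendment with no new procedure, since the month-12 visit is already scheduled. The downside is that the reported GFR change may look less favourable and more variable if anyone is stopped early.
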